### **6.2.4 Treatment Exposure and Compliance**

#### **6.2.4.1 Treatment Exposure**

Treatment exposure data will be summarized and analyzed for the SAF population.

Duration of total exposure to fenfluramine hydrochloride (i.e., time on treatment (in days)) will be calculated per subject as the number of days with IMP intake during the trial, and will be summarized using n, mean, standard error, median, minimum, Q1, Q3 and maximum.

This will be calculated as:

$$\text{Date of last IMP intake} - \text{Date of first IMP intake} + 1$$

Time on treatment will be summarized by treatment group.

#### **6.2.4.2 Compliance**

Study medication is to be administered twice daily, and compliance is recorded in the eDiary as full (both doses), partial (less than full daily dose) or missed (both doses) each day. From this,

---

compliance will be calculated by assuming that a missed dose=0% of dose consumed, partial=50% of dose consumed, and full=100% of dose consumed. For each subject, a daily compliance score will be thus obtained.

Compliance will be summarized for the SAF and mITT populations over the course of T+M and Maintenance only, reported by treatment group.

### **6.2.5 Prior and Concomitant Medications and Therapies**

Medication (collected on the prior/concomitant medication eCRF page) will be coded using the World Health Organization Drug Dictionary (WHO-DD).

The following algorithm will be used to define prior and concomitant:

Concomitant medications will be defined as those medications that were initiated after study drug administration or those that were ongoing at the time of study drug administration.

The medication will be assumed to be prior medication if it cannot be definitively shown that the medication did not start or continue during the treatment period.

If the start date or stop date of a medication is partially missing, the date will be compared as far as possible with the date of the start of administration of study drug. The following approach will be taken:

- If the start date of medication is complete and occurs on or after the day of the first dose, the medication will be assumed concomitant. If the start date occurs prior to the first dose date but the end date is on or after the first dose date or the medication is recorded as ongoing, the medication will be considered concomitant.
- If the start day is missing but the start month and year are complete, a medication will only be excluded as being concomitant if the start month/year is before the month/year of study drug administration and if the stop date (either full date, month and year if missing day, or year if missing month and day) is before study drug administration.
- If the start day and month are missing but the start year is complete, a medication will only be excluded as concomitant if the start year is before the year of study drug administration and if the stop date (either full date, month and year if missing day, or year if missing month and day) is before study drug administration.
- If the start date is completely missing and the stop date is prior to first dose or completely missing, the medication will be assumed to be a prior medication.

Medication will be summarized and sorted alphabetically separately for prior and concomitant medication by Anatomical Therapeutic Chemical (ATC) categories (Level 2: pharmacological or therapeutic subgroup and Level 3: chemical or therapeutic or pharmacological subgroup) and WHO-DD drug code. For each medication the number and percentage of subjects will be displayed.

Summary tables will be presented on SAF population.

All prior and concomitant medications/treatments will be listed for the enrolled population.

---

### 6.2.6 Prior and Concomitant Antiepileptic Treatment

Treatments (collected on the prior/concomitant antiepileptic treatment eCRF page) will be coded using the World Health Organization Drug Dictionary (WHO-DD).

Prior and concomitant antiepileptic will be defined and analyzed for the SAF similar to concomitant medications as described in [section 6.2.5](#).

All prior and concomitant antiepileptic treatments will be listed for the enrolled population.

### 6.2.7 Medical History

Medical history will be summarized and sorted alphabetically, by primary System Organ Class and Preferred Term coded via the most recent version of Medical Dictionary for Regulatory Activities (MedDRA). The number and percentage of subjects will be displayed for each System Organ Class and Preferred Term within treatment group.

Medical history will be presented for the SAF population.

All prior and concomitant medical history data of subjects will be listed for the enrolled population.

## 6.3 EFFICACY ANALYSIS

The analysis of the primary and secondary efficacy parameters will be performed on the mITT population, except where noted.

The primary and key secondary efficacy analyses will be repeated on the PP Population if there are substantial differences between the makeup of the mITT and PP population, in order to assess the impact of major protocol deviations on the key inference.

All primary and key secondary variables will be analyzed for data obtained for the T+M period, and will be repeated for data obtained during the M period only.

### 6.3.1 Primary Efficacy Analysis

The primary efficacy endpoint is the change in the mean convulsive seizure frequency (MCSF) per 28 days between the Baseline and T+M periods. For each subject, the CSF will be calculated from all available data collected during the Baseline and T+M Periods, and the treatment group mean convulsive seizure frequency per 28 days (MCSF) will be calculated for the baseline and T+M period.

The baseline period is the 42 days immediately preceding the Randomization visit and the T+M period is planned for 14 weeks. However, actual durations will be computed for each subject based on the individual subject's start and stop dates for each period, except that if the baseline period is longer than 42 days, the average for the baseline period will be taken over the 42 days immediately preceding the Randomization visit.

The convulsive seizure frequency will be counted from the daily diary records provided by the Subject or Parent/Caregiver.

For any individual subject, the convulsive seizure frequency per 28 days during the baseline period (CSFB) will be derived as follows:

$$CSF_B = \frac{28 \times \text{Total number of convulsive seizures during the Baseline Period}}{\text{Total number of days in the Baseline Period with nonmissing diary data}}$$

For each treatment group, the mean is obtained by averaging over the subjects in the treatment group.

Similarly, for each subject, the convulsive seizure frequency per 28 days for the T+M period ( $MCSF_{T+M}$ ) is derived as below:

$$CSF_{T+M} = \frac{28 \times \text{Total number of convulsive seizures in the T + M period}}{\text{Total number of days in the T + M period with nonmissing diary data}}$$

The percentage change from baseline for any individual subject will be estimated by

$$(CSF_{T+M} - CSF_B) * 100 / CSF_B$$

The difference from baseline will be estimated by  $CSF_{T+M} - CSF_B$ .

Corresponding treatment group means are designated with “M” preceding the quantity. For each treatment group, descriptive statistics for MCSF during baseline, T+M and M only, as well as the differences and % changes from baseline, will include the number of observations, mean, standard deviation, median, minimum and maximum, overall and by age group (<6 years, ≥6 years).

### 6.3.1.1 Primary Analysis

#### T+M Period:

The primary analysis will compare the ZX008 0.8 mg/kg/day group to the placebo group using a two-sided test at the  $\alpha=0.05$  level of significance.

The primary endpoint ( $CSF_{T+M}$ ) will be analyzed using an analysis of covariance (ANCOVA) model with treatment group (three levels) and age group (< 6 years, ≥6 years) as factors, log baseline  $CSF_B$  as a covariate and log  $CSF_{T+M}$  as response. Treatment group mean differences from placebo will be estimated via least squares means from the analysis model along with 95% confidence intervals and associated 2-sided p-values. Estimated treatment differences and CI endpoints will be exponentiated for presentation.

The null hypothesis

$$H_0: \mu_{Z0.8} - \mu_P = 0,$$

will be tested against the alternative

$$H_A: \mu_{Z0.8} - \mu_P \neq 0,$$

where  $\mu_{Z0.8}$  and  $\mu_P$  represent the ZX008 0.8 mg/kg and Placebo group means (on the log scale), respectively.

Rejection of the null hypothesis in favor of the alternative, in the presence of a statistically significantly smaller mean convulsive seizure frequency for the treatment group compared to the placebo group, (two-sided p-value < 0.05) will be regarded as evidence of a treatment benefit in favor of the 0.8 mg/kg group.

Sample SAS code for the ANCOVA described above is as follows:

```
proc glm data=temp;
  class agegrp trtp;
```

---

```
model csftm = bcsf agegrp trtp / SS3;  
lsmeans trtp / pdiff stderr;
```

where trtp = randomized treatment group (with codes 1, 2, 3 indicating placebo, 0.2 mg, and 0.8 mg groups).

```
bcsf = log( CSFB ),  
csftm = log( CSFT+M + 1 )  
agegrp = age group.
```

Additional statements may be used to obtain estimates and associated 95% confidence intervals. Endpoints of the CIs may be exponentiated to obtain CI on the original scale. Fitted values and residuals may be plotted to check model assumptions.

Since the ANCOVA used in the primary analysis relies on assumptions of normality, the primary endpoint will also be analyzed using a nonparametric method that does not require as stringent assumptions. A nonparametric ANCOVA will be used to analyze the data, with ranks of the baseline CSFB as a covariate and ranks of CSFT+M as response, and the results will be used to assess the primary objective. If normality assumptions are not met, the results of the nonparametric test will be used to assess the primary objective.

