**SCOPE**

Zogenix is conducting two identical Phase 3 studies of ZX008, Study ZX008-1501 (Study 1501) and Study ZX008-1502 (Study 1502). Study 1501 is being conducted in the United States and Canada; Study 1502 is being conducted in Europe and Australia. Approximately 120 subjects with Dravet syndrome, a rare form of pediatric epilepsy, are planned for randomization into each study in three treatment groups: 0.2 mg/kg/day ZX008, 0.8 mg/kg/day ZX008 and placebo (n=40/group). Due to slow enrollment into both trials, the databases for the two trials will be combined and the first 120 subjects to be randomized will be analyzed and reported as Study 1, covered by this Statistical Analysis Plan (SAP). Additional randomized subjects (over N=120) are intended to be reported as Study 2, and a separate SAP will cover those analyses. Primary and key secondary analyses in the Study 1 SAP remain as stated in the protocols and as described in the Study 1 draft SAP with some changes delineated in this SAP based on FDA feedback.

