**STATISTICAL ANALYSIS PLAN**  
Zogenix International Limited  
ZX008 Study 1

Upon completion of the Baseline Period, subjects who qualify for the study will be randomized (1:1:1) in a double-blind manner to receive 1 of 2 doses of ZX008 (0.2 mg/kg/day, 0.8 mg/kg/day; 30mg/day maximum) or placebo. The randomization will be stratified by age (<6 years, ≥6 years) to ensure balance across treatment arms, with the target of 25% of subjects in each age group. Subjects will be assigned a randomization number by the IVR/IWR system upon confirmation that subject qualifies for enrollment in the Titration Period. Once a randomization number is assigned to a subject, the site will record the subject's initials and identification number on the corresponding study drug bottles. Each bottle will contain the assigned treatment (ZX008 0.2 mg/kg/day, ZX008 0.8 mg/kg/day, or placebo). ZX008 and placebo will be identical, thus rendering the study drug and placebo indistinguishable. The randomization scheme and block size for Studies 1501 and 1502 are the same, so combination of the data from the two studies will not skew the intended randomization into the three treatment groups.

Study 1 will include the first 120 randomized subjects from Study 1501 and Study 1502. Once enrollment in Study 1 is complete (i.e., when subjects 1 to 120 are randomized), the subjects will be treated and followed through their last study visit. After the last of the subjects in Study 1 has either discontinued or completed treatment, the database will be locked for those subjects and Study 1 be reported as per this SAP.

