### **3.4 RANDOMIZATION**

Treatment assignments are assigned independently within Study 1501 and Study 1502. Specifically, each trial assigns treatments using randomized permuted blocks; i.e., treatments are assigned in blocks to ensure exact balance among treatments within each block. The blocking is applied across the entire trial such that newly enrolled subjects are randomized to the next available treatment regardless of the site or country where they enroll. This approach assures balance among treatment groups within each trial at any point during enrollment. Combining data from two trials means that two sets of randomized blocks will be used, which would have approximately the same effect as doubling the block size in a single trial. Increasing the block size is expected to have little impact on a trial of 120 subjects. Moreover, combining the first 120 randomized subjects from Study 1501 and Study 1502 to create Study 1 preserves balance among the three treatment groups in each of Study 1 and Study 2, yielding approximately 40 subjects per arm, the number required to maintain full statistical power.

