**Statistical Analysis Plan**

Sponsor: Zogenix International Limited; Protocol No.: ZX008 Study 2 (ZX008-1501 and ZX008-1502)

Table	14.1.5.2	Compliance to IMP Intake – Safety Population
Table	14.1.5.2a	Compliance to IMP Intake (Japan) – Safety Population
Table	14.1.5.2b	Compliance to IMP Intake (Non-Japan) – Safety Population
	14.2	Efficacy, pharmacokinetics, and pharmacodynamics
	14.2.1	Efficacy – ZX008 0.8 and 0.2 mg/kg/day vs Placebo
Table	14.2.1.1.1	Convulsive Seizure Frequency per 28 Days : Summary Statistics – mITT Population
Table	14.2.1.1.1a	Convulsive Seizure Frequency per 28 Days : Summary Statistics (Japan) – mITT Population
Table	14.2.1.1.1b	Convulsive Seizure Frequency per 28 Days : Summary Statistics (Non-Japan) – mITT Population
Table	14.2.1.1.2	Convulsive Seizure Frequency per 28 Days, by Age Group : Summary Statistics – mITT Population
Table	14.2.1.1.2a	Convulsive Seizure Frequency per 28 Days, by Age Group : Summary Statistics (Japan) – mITT Population
Table	14.2.1.1.2b	Convulsive Seizure Frequency per 28 Days, by Age Group : Summary Statistics (Non-Japan) – mITT Population
Table	14.2.1.1.3	Convulsive Seizure Frequency per 28 Days, by Sex : Summary Statistics – mITT Population
Table	14.2.1.1.3a	Convulsive Seizure Frequency per 28 Days, by Sex : Summary Statistics (Japan) – mITT Population
Table	14.2.1.1.3b	Convulsive Seizure Frequency per 28 Days, by Sex : Summary Statistics (Non-Japan) – mITT Population
Table	14.2.1.1.4	Convulsive Seizure Frequency per 28 Days, by Race : Summary Statistics – mITT Population
Table	14.2.1.1.4a	Convulsive Seizure Frequency per 28 Days, by Race : Summary Statistics (Japan) – mITT Population
Table	14.2.1.1.4b	Convulsive Seizure Frequency per 28 Days, by Race : Summary Statistics (Non-Japan) – mITT Population
Table	14.2.1.2	Convulsive Seizure Frequency per 28 Days : Parametric Analysis – mITT Population
Table	14.2.1.2a	Convulsive Seizure Frequency per 28 Days : Parametric Analysis (Japan) – mITT Population
Table	14.2.1.2b	Convulsive Seizure Frequency per 28 Days : Parametric Analysis (Non-Japan) – mITT Population
Table	14.2.1.2c	Convulsive seizure frequency per 28 days During Double-blind Treatment for Study 2 by Original Randomized Study (1501/1502): Parametric Analysis – Study 2 - mITT Population
Table	14.2.1.2.1	Convulsive Seizure Frequency per 28 Days, by Age Group : Parametric Analysis – mITT Population

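### The two studies were randomised separately, but the pooled primary ANCOVA has no study factor: the test stays valid but gives up a little precision if study is prognostic

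*SAP*

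**What the plan says.** **Allocation.** Study 1 SAP section 3.4 states: "Treatment assignments are assigned independently within Study 1501 and Study 1502". It adds that "each trial assigns treatments using randomized permuted blocks" and that "Combining data from two trials means that two sets of randomized blocks will be used". Section 3.1 gives the other design factor, age: "The randomization will be stratified by age (<6 years, ≥6 years) to ensure balance across treatment arms". Allocation is "randomized (1:1:1) in a double-blind manner" in both studies. Study coincides with region; the Scope says: "Study 1501 is being conducted in the United States and Canada; Study 1502 is being conducted in Europe and Australia". The Study 2 SAP adds Japan to Study 1502.

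**Analysis.** Section 6.3.1.1 of the Study 1 SAP and section 8.1 of the Study 2 SAP specify the same "model with treatment group (three levels) and age group", with log baseline frequency as covariate. The sample SAS code in both places lists baseline, age group and treatment only. The responder logistic regression uses treatment and age group. The longest interval is compared by an unstratified Wilcoxon rank-sum test.

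**Study or region elsewhere.** Both SAPs pool across sites and leave regional differences to optional exploration (Study 1 section 6.1.9, Study 2 section 6.6). Neither the Study 1 supplementary analyses (6.3.1.2) nor its list of efficacy tables (Appendix 1) contains a by-study or study-adjusted analysis. The Study 2 index has tables by original study, for example Table 14.2.1.2c, titled in part "for Study 2 by Original Randomized Study (1501/1502): Parametric Analysis", and Tables 14.2.15.1 and 14.2.15.3. None is described as a pooled estimate adjusted for study.

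**The concern.** The plan adjusts for one factor that governed allocation, age, and omits the other, study, without giving a reason. Section 3.4 defends pooling on treatment balance and block size. That answers a question about allocation. It does not say whether the analysis should reflect the separate schedules.

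Balance within study is the reason the omission matters. Blocking removes the between-study component from the true variance of the treatment difference. A model without study leaves that component in the residual, so the reported standard error is larger than the true one whenever study is prognostic. The cost is precision. It carries some weight because formal testing is strictly serial over six steps, so one missed step stops every later test, including all the 0.2 mg/kg/day comparisons.

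**Working it through.** **Plan's own figure.** Inputs from section 6.1.10: difference 40 percentage points, SD 55, two-sided alpha 0.05, 90% power. The normal formula gives 40 per arm. Power at 40 per arm is 90.2% (normal) or 89.5% (t, 78 df), so the stated size reproduces.

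**Overstatement of the standard error.** Let R² be the share of residual variance, after baseline and age, that study explains. With allocation balanced within study:

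- true SE = 55·√(1−R²)·√(2/40)
- SE reported without study ≈ 55·√(2/40) = 12.30
- ratio = 1/√(1−R²)

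For R² = 5%, the true SE is 12.30 × √0.95 = 11.99 and the ratio is 1.026.

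**Power with and without the term.** Take two arms of 40, each split equally between the studies, with total SD 55 and difference 40.

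- *Without study:* the estimate has the true SE above. The residual variance is 55²(1−R²)/78 times a non-central chi-square with 78 df and non-centrality 80·R²/(1−R²). The critical value is t = 1.991.
- *With study:* the usual non-central t with 77 df and non-centrality 40/(true SE).
- *Implied gap between study means*, in within-study residual SDs: 2·√(R²/(1−R²)).

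| Assumed R² | Implied gap (SD) | SE overstated by | Power without study | Power with study | Gain (points, before rounding) |
|---|---|---|---|---|---|
| 1% | 0.20 | 0.5% | 89.5% | 89.8% | 0.2 |
| 2% | 0.29 | 1.0% | 89.7% | 90.0% | 0.4 |
| 5% | 0.46 | 2.6% | 90.0% | 90.9% | 0.9 |
| 10% | 0.67 | 5.4% | 90.6% | 92.3% | 1.7 |

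**Check nearer the planned model.** This was a simulation of 120 subjects in three arms, with separate permuted blocks by study and age. The ANCOVA on baseline, age and treatment was fitted with and without study (4000 runs per cell, effect 40/55 SD). Assumed because the SAP does not give them: blocks of six, 25% of subjects under 6 years, a 50:50 split between studies, and the between-study gap.

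| Assumed gap (residual SD) | Type I error without / with study | Power without / with study |
|---|---|---|
| 0 | 0.048 / 0.047 | 0.89 / 0.89 |
| 0.25 | 0.047 / 0.048 | 0.90 / 0.90 |
| 0.5 | 0.039 / 0.047 | 0.89 / 0.90 |
| 1.0 | 0.027 / 0.049 | 0.84 / 0.89 |

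Bias was about zero in every cell, and a 70:30 split gave similar results.

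**Cost.** The planned model has 120 − 5 = 115 residual degrees of freedom; with study it has 114.

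**The case against.** The strongest reply is that nothing is invalid. Allocation is 1:1:1 in both studies, so study cannot confound treatment, and any error is towards conservatism. The documents give no between-study difference, log baseline frequency may absorb part of one, and a gap large enough to cost five power points (1.0 residual SD) is only an assumption. The illustrative power figures also come from a two-arm comparison of percentage change, not from the log-scale three-arm ANCOVA. All of this stands, and it limits the point to efficiency.

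Three stronger readings are tempting and are not supported:

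- **Bias or false positives.** A reader might infer that ignoring a randomisation factor biases the estimate or inflates type I error. The simulation shows neither.
- **A larger power gain.** A reader might set the adjusted power against the 89.5% from the sample-size calculation and find a gain of up to 92.3 − 89.5 = 2.8 points. But 89.5% is the power when study explains nothing. With balance within study, the unadjusted estimate already has the smaller true variance and only its reported SE is too large. The proper comparator at R² = 10% is 90.6%, so the gain is 1.7 points.
- **Chance imbalance at the 120-subject cut.** Blocks run across each whole trial, so imbalance by study is confined to incomplete blocks. It is minor, and a large imbalance would contradict the near-balance on which the standard-error argument rests.

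The reply that the plan already deals with study goes only part of the way. The Study 2 by-study tables and the Japan/non-Japan subgroups describe differences and leave the primary test unchanged. Study 1 has no such tables. Japan does not strengthen the case either: it lies within Study 1502, so a two-level study factor cannot separate it from Europe and Australia.

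**Conclusion.** The omission is real, and it is inconsistent with the plan's own adjustment for age. The planned test is unbiased and does not inflate type I error. It is conservative if study predicts outcome after baseline and age. For an assumed 1 to 10% of residual variance, the standard error is overstated by about 0.5 to 5.4% and about 0.2 to 1.7 power points are given up; up to 5%, the loss is below one point. With no study effect nothing is lost, and adding the term would cost one degree of freedom. This is an inexpensive gain in efficiency and consistency and does not threaten the primary conclusion. The size depends wholly on the assumed R² and on near-balance within study.

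**What to change.** In both SAPs, prespecify originating study (1501/1502) as a class factor in:

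- the primary ANCOVA, in the text and the SAS code, and hence the same comparison for 0.2 mg/kg/day;
- the rank ANCOVA that serves as its fallback;
- the responder logistic regression.

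The Wilcoxon rank-sum test for the longest interval has no model to take a factor, so replace it with a study-stratified (van Elteren) test. Keep the Study 2 by-study tables as descriptive.

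The cost is one class variable, one residual degree of freedom out of 115, and a changed procedure for one endpoint. The change has to be fixed before the data concerned are unblinded. Where that has already happened, the same model can be reported only as a supportive analysis labelled post hoc.

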### 6.3.2.3 Longest Interval between Convulsive Seizures

The longest interval between convulsive seizures will be analyzed.

For each subject, the longest interval between convulsive seizures will be calculated over the entire T+M period. This will be derived as the maximum of the number of days between consecutive convulsive seizures. The intervals between consecutive convulsive seizures will be calculated as below, after which the longest interval between convulsive seizures will be derived.

If a subject has two consecutive days of missing diary data, the current seizure-free interval will be ended on the first date of missing diary data, and a new one begun on the next date that diary data are available and no seizure occurs. [In that case, for purpose of calculation of this variable, all intervening days, after the 2nd day, with missing diary data, will be assumed to have a convulsive seizure occurrence, until the first available date with non missing diary data.]

Let Date0 (=Day1) be the first day of treatment. If convulsive seizure occurs on five days having dates as Date1, Date2, Date3, Date4 and Date5, where  $Date5 > Date4 > Date3 > Date2 > Date1 \geq Date0$ , and let LDT = Last date of treatment in the maintenance period, where  $LDT \geq Date5$ , then the time interval between convulsive seizures will be calculated as follows:

$$I1 = Date2 - Date1$$

$$I2 = Date3 - Date2$$

$$I3 = Date4 - Date3,$$

$$I4 = Date5 - Date4.$$

For completeness, we calculate the time to the first seizure as

$$I0 = Date1 - Date0,$$

and the time from the last seizure to end of treatment as

$$I5 = LDT - Date5.$$

Here the duration of the longest interval = Maximum (I0, I1, I2, I3, I4, I5).

If the subject does not experience a seizure during treatment, then the last available diary date will be used to compute the duration of the longest interval as follows:

The longest interval=last available diary date – Date0

The median time of the longest convulsive seizure-free interval will be presented. Additional summary statistics will be presented, including mean, minimum, maximum, the 25th and 75th percentiles, 95% confidence intervals on the difference in medians between groups (Hodges-Lehman estimator).

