### 3. Endpoints

#### 3.1. Primary Efficacy Endpoint

The change from baseline in the mean convulsive seizure frequency (MCSF) in combined Titration and Maintenance Periods (T+M) in the ZX008 0.8 mg/kg/day group compared to the placebo group.

The primary endpoint will be assessed using a parametric analysis of covariance (ANCOVA). MCSF will be log-transformed prior to analysis. If the assumptions of the parametric ANCOVA model are not met, the primary endpoint will be assessed using a nonparametric ANCOVA where MCSF is rank-transformed prior to analysis.

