### Percentage Reduction from Baseline

The ANCOVA employed in the primary analysis uses log CSFT+M as the response adjusts for baseline seizure frequency by incorporating CSFB as a factor in the model. The alternative approach described here calculates the percentage change in CSF from baseline directly and uses that quantity as the response variable in an ANCOVA model. Specifically, the ANCOVA will use the percentage change from the T+M period to baseline as the response variable, baseline CSF as a covariate, and treatment and age stratum as classification factors. The analyses will be repeated for the M period only using the baseline as covariate.

If the distributional assumptions for the parametric analysis are not met, a nonparametric ANCOVA will be used for the ranks of the dependent variable as response, using the ranks of the baseline as covariate.

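### The primary response is log CSF in the prose and log(CSF + 1) in the code, and the exponentiated result of the coded model is a ratio of CSF + 1, not a figure on the original scale

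*SAP*

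**What the plan says.** The Study 1 SAP (6.3.1.1 Primary Analysis) and the Study 2 SAP (8.1, Primary Analysis) describe the model in the same way. The prose takes log baseline CSF "as a covariate and log $CSF_{T+M}$ as response". It then says "Estimated treatment differences and CI endpoints will be exponentiated for presentation".

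The code follows under the line "Sample SAS code for the ANCOVA described above is as follows", yet it defines the response as "csftm = log( CSFT+M + 1", with the constant inside the log. The covariate is log baseline CSF without a constant in both prose and code, so the mismatch concerns the response only. After the code, both SAPs add "Endpoints of the CIs may be exponentiated to obtain CI on the original scale".

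Other descriptions of the model also leave out the constant:

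- Percentage Reduction from Baseline, in both SAPs: "The ANCOVA employed in the primary analysis uses log CSF T+M as the response".
- Study 2 SAP, 3.1 Primary Efficacy Endpoint: "MCSF will be log-transformed prior to analysis".
- Study 2 SAP, 6.4 Missing Data: sensitivity analysis S1 again names the log of CSF as response.

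Subjects with zero seizures on treatment are expected. The longest-interval endpoint has a rule for them ("If the subject does not experience a seizure during treatment, then the last available diary date will be used"), and the Study 2 SAP makes a 100% reduction an additional secondary endpoint.

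**The concern.** Under Criteria for Establishing Efficacy, both SAPs make the log-transform analysis in the mITT population the main criterion. That model has two definitions, and they do different things.

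If the prose is programmed, log(0) is missing and PROC GLM leaves the record out. The subjects lost are those who became seizure-free, although the mITT definition requires only a dose and a week of diary data.

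If the code is programmed, nobody is lost. However, exponentiating a difference of log(CSF + 1) gives a ratio of geometric means of CSF + 1. One whole seizure per 28 days has been added to each side, which pulls the ratio towards 1, most where on-treatment frequency is low. The headline estimate and its interval would carry a label that the model does not support.

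**Working it through.** **The plan's own figure.** The only reproducible figure nearby is the sample size (Study 1 SAP 6.1.10; Study 2 SAP 2.5): a 40-point difference, SD 55, two-sided 0.05, 90% power. n = 2 × (1.960 + 1.282)² × 55² / 40² = 39.7, so 40 per arm, with power 0.902. It reproduces. It is on the percentage-change scale and says nothing about the size of the present point. The SAPs state no expected back-transformed reduction.

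**Formula.** Let c be the placebo on-treatment CSF per 28 days and r the true ratio of active to placebo, with c common to all subjects.

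- Exponentiated difference under the code: (rc + 1)/(c + 1).
- Reduction it appears to show: 1 − (rc + 1)/(c + 1) = (1 − r) × c/(c + 1).
- Shortfall against the true reduction 1 − r: (1 − r)/(c + 1).

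**Inputs.**

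- c is an assumption. The only guide in the SAPs is the set of baseline bands: below 10, 10 to 50, above 50.
- The external trial quoted for sample size had reductions of 39% and 13%: r = 0.61/0.87 = 0.70, a relative reduction of 29.9%.
- The design difference of 40 points on a 13% placebo reduction gives r = 0.47/0.87 = 0.54, a relative reduction of 46%.
- 40% and 60% are added as assumptions to show the range.

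**Example.** With r = 0.54 and c = 10, the ratio is (5.4 + 1)/11 = 0.582, an apparent reduction of 41.8%. The shortfall is 0.46/11 = 4.2 points.

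| True reduction | c = 5 | c = 10 | c = 20 | c = 50 |
|---|---|---|---|---|
| 29.9% | 24.9 (5.0) | 27.2 (2.7) | 28.5 (1.4) | 29.3 (0.6) |
| 40% | 33.3 (6.7) | 36.4 (3.6) | 38.1 (1.9) | 39.2 (0.8) |
| 46% | 38.3 (7.7) | 41.8 (4.2) | 43.8 (2.2) | 45.1 (0.9) |
| 60% | 50.0 (10.0) | 54.5 (5.5) | 57.1 (2.9) | 58.8 (1.2) |

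Cells give the apparent reduction in per cent, with the shortfall in points in brackets.

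**Check with varying subjects.** The coded ANCOVA was simulated without the age factor, 300 trials per setting. The assumptions were two arms of 40, log-normal subject rates, Poisson counts over 42 and 98 days, and a 13% placebo reduction. True reductions ran from 30% to 60%. The shortfall against the true log-rate contrast was about 6 to 14 points at a median baseline rate of 5, 4 to 8 at 10, 2 to 5 at 20, and 1 to 2.5 at 50. These are somewhat above the table, because the placebo level is 13% below baseline and subjects differ.

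**The prose branch.** In the same simulation at a median of 5 and a true 60% reduction, 3.9% to 5.9% of subjects had no seizures on treatment. Dropping them gave 57.4% and 56.1% against true contrasts of 60.3% and 60.4%. At medians of 20 or more, fewer than 1% had none and the change was below 1 point.

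**Baseline bands.** Both SAPs repeat the analysis by baseline frequency category. A constant true reduction of 60% would appear as 50%, 57% and 59% at c = 5, 20 and 70, a gradient made by the constant alone.

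**The case against.** The strongest reply is that this is a slip between prose and code with little consequence. The +1 is the only handling of zeros in either SAP, so the code is the natural reading and the loss of seizure-free subjects is a possible programming error, not the likely plan. The two harms also exclude each other: the prose version has no dilution, and the code version loses nobody. Efficacy rests on the significance test. Equal distributions give a difference of zero on either scale, and the dilution can only shrink a benefit. The rank-based ANCOVA is untouched, because adding 1 and taking logs leaves ranks unchanged. Percentage change is derived separately from untransformed CSF, with its own summaries, its own ANCOVA and the responder analyses.

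All of that stands, and it limits the point. A reader might infer that the reported seizure reduction will be several points too small. The documents do not support that as a flat statement. They give neither the on-treatment frequency nor the true effect, and they do not say that the exponentiated value will be quoted as a percentage reduction. The understatement also needs the code to be the version that is run.

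The reply does not remove the contradiction in the deciding model, nor the scale label, which is wrong for the coded response at any seizure frequency. The p-value can also depend on which response is run.

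**Conclusion.** The point holds as an inconsistency in the definition of the primary response and as a mislabelled scale, in both SAPs. The prose version cannot be computed for subjects whom the plans expect to exist. The coded version can, but its exponentiated estimate and interval are ratios of CSF + 1.

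The numerical size is conditional on the code being followed and on the figure being read as a reduction in seizure frequency. For effects near the SAPs' planning figures (about 30% to 46%), the shortfall is about 3 to 4 points at 10 seizures per 28 days, 1 to 2 at 20, and under 1 at 50. It reaches 5 points or more at about 5 per 28 days, or near 10 with a true reduction of about 60%. These values assume a common placebo level; variation between subjects raises them somewhat. The type I error is not affected, and the direction is against the drug. This should be corrected, but it does not threaten the primary test.

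**What to change.** 1. State log(CSF + 1) in T+M as the response wherever the prose describes the primary model: 6.3.1.1 and Percentage Reduction from Baseline in the Study 1 SAP; 3.1, sensitivity analysis S1 in 6.4, 8.1 and Percentage Reduction from Baseline in the Study 2 SAP. Keep the p-value from that model. Simply deleting the +1 from the code is not a fix, because it loses the seizure-free subjects.
2. Delete the original-scale wording and label the exponentiated estimate and its 95% CI as a ratio of (CSF + 1), in the text and in the table footnotes.
3. Optionally add a supplementary estimate on the CSF scale, (exp(LSM active) − 1)/(exp(LSM placebo) − 1), with a bootstrap or delta-method CI. State that it is approximate and evaluated at the mean covariate values: in simulation with a true ratio of 0.40 it gave 0.410 to 0.419. Its interval need not agree with the model's test, so it should not replace the labelled ratio.

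The cost is SAP wording, table footnotes and, for item 3, one post-estimation step. The coded test is unchanged. The Study 2 SAP says Study 1 has been reported, so there the step is to confirm which response was run and to correct the label.
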